- Dietary Counseling from research dietitian including review of diet reports from Healthwatch 360 app – 15 minutes

Summary of Final Site Visit 4 (Final Site Visit) (12 months)

- Urine pregnancy test (if applicable – i.e. a female of child bearing potential)
- Weight and BMI calculation
- Check skin behind ears (visual inspection to ensure appears healthy)
- Waist and hip measurements
- Fasting Insulin level
- High Sensitivity C-Reactive Protein
- Lipid Panel
- Oral Glucose Tolerance Test (OGTT)
- Pulse rate and blood pressure
- Quality of life survey (Duke University IWQOL – <http://www.qualityoflifeconsulting.com/iwqol-lite.html>)
- DXA Scan (whole body scan)
- Coordinator asks participant to complete adverse event monitoring questionnaire.
- Audiogram test including otoscope examination of the ear canals.

Other activities at Visit 4 (12 months):

- The study participant will return the investigational device.

Frequency of Follow-Up Appointments

Visits in person at: enrollment (0 months); 3 months; 6 months; and 1 year. Telephone follow up at: weeks 2; months 1 & 9; and as required on an ad hoc basis. There will also be the facility to bring subjects in for review should concerns be raised after the telephone review – e.g. concern re skin irritation behind the ear. Study participants are also free to contact (call or email) study personnel at any time with any issues or inquiries.

Primary Outcome Measures (At 12 months)

- The difference in mean weight loss between the active-product and placebo-treated groups is at least 5% total body weight lost (TBWL), and the difference is statistically significant.
- The proportion of participants who lose 5% or more of baseline body weight in the active-product group is at least 35% and is approximately double the proportion in the placebo-treated group; the difference between groups is statistically significant.

Secondary Outcome Measures (At 12 months)

- The difference in mean percent loss of baseline total body fat in the active versus placebo treated groups. (As measured by means of a whole body DXA scan– see Appendix 4).
- The proportion of subjects who lose at least 5% of baseline total body fat in the active versus placebo treated groups. (As measured by a whole body DXA scan).
- The difference in mean percent loss of baseline truncal body fat in the active versus placebo treated groups. (As measured by a whole body DXA scan).

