Methods: Primary Aims

For total body weight loss (TBWL) as a continuous measure, we will use a two-sample t-test to examine the differences between the control and active treatment groups at each time period. We will also build one-sided confidence intervals to test whether the difference between groups exceeds a superiority margin of 5%. As a secondary analysis, we will also use a linear regression with TBWL as the dependent variable and group and other covariates of interest (gender, age, etc.) as independent variables. To assess any longitudinal effects, we will use a linear mixed effects model for weight over time, with fixed covariates for baseline weight, time, group, and a time / group interaction, and a random intercept to account for within-subject correlation. We will use a one-sided exact binomial test to determine if the response rate in the treatment group significantly exceeds 35%, with response defined by a loss of at least 5% of their body weight at the 12-month follow-up. We will also use Fisher's exact test to compare the response rates in each group, and, as a secondary analysis, will consider the use of a logistic regression to control for any other covariates of interest. To investigate possible longitudinal trends, we will fit a logistic mixed effects model, similar to the linear mixed effects model described above.

Methods: Secondary Aims

For each continuous and categorical variable at each time point, we will use a two-sample t-test and Fisher's exact test, respectively. Summary statistics (mean, standard deviation, quantiles, counts, and percentages) and plots will be produced for all demographic and study outcomes. We will investigate the effectiveness of the device by usage by including usage time as a continuous covariate in a linear model for TBWL. CTRI Biostatistics Core personnel will conduct all analyses using the latest version of R (R Foundation for Statistical Computing, Vienna, Austria. <http://www.R-project.org/>). No alpha spending function is applied to adjust for multiple comparisons across the secondary aims, and no claims will be made based on any of the secondary endpoints, which are instead viewed as hypothesis generating endpoints.

Missing Data

The primary hypotheses will be tested on the intent-to-treat population. A sensitivity analysis will be

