performed with the binary weight loss endpoint. This analysis will include a best-case scenario (assuming subjects with missing values have all lost over 5% body weight), a worst-case scenario (assuming no subjects with missing values have lost over 5% body weight), and a tipping point analysis (as described in Yan¹). We will check the assumption that the data is missing completely at random, and use multiple imputation techniques to reduce bias in the estimation of the treatment effect. Missing data will be clearly reported and included in tables.

Power Calculation

The primary outcomes are TBWL from the start of treatment until the 12-month mark and the number of subjects who lose at least 5% of their baseline total body weight. We will power both of these tests at the 0.025 significance level (a Bonferroni correction to maintain a family-wise error rate of 0.05 in our primary analysis). For TBWL, we will test the following null and alternative hypothesis:

$$\begin{aligned} H_0: \mu_t - \mu_c &\leq 5\% \\ H_1: \mu_t - \mu_c &> 5\% \end{aligned}$$

where μ_t and μ_c are the treatment and control mean TBWL in the ITT population. We will use a one-sided two-sample t-test to determine if there is a statistically significant difference in TBWL between our control and treatment arms beyond a superiority margin of 5%. With a total sample size of 90 subjects (30 sham and 60 active treatment), this t-test will have 80% power at the $\alpha = 0.025$ significance level to detect an effect size of $d = 0.63$. Assuming a similar standard deviation of TBWL as the ReShape trial (7.5%), this translates to a detectable difference in TBWL between the treatment and control groups of 4.75%. Assuming this same standard deviation, a two-sample superiority test will have 80% power assuming that the true difference between groups is 6.33%.

For the proportion of treatment subjects who lose at least 5% of their baseline total body weight, we will test the following null and alternative hypothesis:

$$\begin{aligned} H_0: P_t &\leq 35\% \\ H_1: P_t &> 35\% \end{aligned}$$

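### The plan gives no single decision rule for the TBWL primary: at the planning values, observed differences from 5.0% to about 8.3% pass one stated rule and fail the other

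*Combined protocol and SAP*

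**What the plan says.** Three places in Section 9 bear on success for the 12-month TBWL primary.

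- **Primary Outcome Measures (At 12 months).** The difference in mean weight loss between arms "is at least 5% total body weight lost (TBWL), and the difference is statistically significant". No null value or confidence limit is mentioned.
- **Statistical Considerations, Methods: Primary Aims.** First an unmargined comparison: "we will use a two-sample t-test to examine the differences between the control and active treatment groups at each time period". Then an addition: "We will also build one-sided confidence intervals to test whether the difference between groups exceeds a superiority margin of 5" percent. The confidence level is not given there, and nothing says which of the two decides.
- **Statistical Considerations, Power Calculation.** The hypotheses are H0: μt − μc ≤ 5% against H1: μt − μc > 5%, with a one-sided t-test "to determine if there is a statistically significant difference in TBWL between our control and treatment arms beyond a superiority margin of 5" percent. On alpha: "We will power both of these tests at the 0.025 significance level". The same paragraph gives a detectable difference of 4.75% and, for the superiority test, 80% power at a true difference of 6.33%.

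**The concern.** The natural reading of the outcome definition has two parts: the difference reaches 5%, and the arms differ significantly. The Power Calculation puts the null at 5% itself, which asks for much more, because the estimate must clear 5% by about two standard errors. An estimate of 6% or 7% would normally meet the first rule and fail the second.

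This is one of two primary endpoints, in a study meant to support regulatory submissions (Section 6). If the deciding rule is not fixed in advance, the verdict on a result between the two thresholds depends on which section is followed. The sample-size justification depends on it too, since the effect needed for 80% power differs between the rules.

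**Working it through.** **Inputs**, all from the Power Calculation: 60 active and 30 sham (88 degrees of freedom), SD of TBWL 7.5 percentage points, one-sided alpha 0.025, margin 5%.

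**1. The plan's own figure.**
- Standard error = 7.5 × √(1/60 + 1/30) = 7.5 × 0.2236 = 1.677.
- By the noncentral t, 80% power needs d = 0.6334, and 0.6334 × 7.5 = 4.75%. The plan's d = 0.63 and 4.75% reproduce, but as a test against zero. A true 4.75% lies inside H0: μt − μc ≤ 5%, so it cannot be a detectable difference for the margin test.

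**2. Observed difference each rule needs.** The critical value t(0.975, 88) is 1.987.
- Outcome definition, with significance read as against zero: significance needs 1.987 × 1.677 = 3.33% (3.82% if 0.025 is taken as two-sided). Both are below 5%, so the 5% condition binds and the rule is met from 5.0%.
- Margin test: 5 + 3.33 = 8.33% (8.29% with a normal critical value).

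Between 5.0% and about 8.3% the first rule is met and the second is not. No result passes the margin test and fails the outcome definition.

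**3. Chance of meeting each rule at a true difference δ.** For the outcome definition this is Φ((δ − 5)/1.677). For the margin test it is the noncentral t with 88 df and noncentrality (δ − 5)/1.677. At δ = 6.33, (6.33 − 5)/1.677 = 0.793 and Φ(0.793) = 0.786. Because the rules are nested, the last column is the simple difference.

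| True δ | Outcome definition | Margin test | Passes the first only |
|---|---|---|---|
| 4.75% | 44.1% | 1.8% | 42.3% |
| 5.00% | 50.0% | 2.5% | 47.5% |
| 6.33% | 78.6% | 12.0% | 66.6% |
| 9.75% | 99.8% | 80.0% | 19.8% |

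Simulation with an estimated SD agrees with these figures to within 0.3 percentage points.

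**4. True difference needed for 80% power.**
- Margin test: 5 + 4.75 = 9.75%.
- Test against zero plus an observed difference of at least 5%: 5 + 0.842 × 1.677 = 6.41%.

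**5. Sensitivity of the band.** The upper edge is 5 + 1.987 × SD × 0.2236.
- SD 5% gives 7.22% and SD 10% gives 9.44%. This SD range is my assumption.
- With all 106 recruits analysed (71/35) at SD 7.5%, the edge is 8.07%.
- The lower edge stays at 5.0% over that SD range, because one-sided significance against zero needs only 2.22% to 4.44%.

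**The case against.** The best reply is that the plan writes only one formal TBWL hypothesis, the one with the 5% margin, and that the outcome definition is looser wording for it. That definition never says observed or point estimate. The responder primary follows the same pattern: its 35% level in the outcome list becomes H0: Pt ≤ 35% in the statistical section. This reading is tenable, and it is a good reason to make the margin hypothesis the default.

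It does not settle the matter. In the responder bullet, significance attaches to the difference between groups and not to the 35% level, and the TBWL bullet is built the same way. A true difference of exactly 5% satisfies the outcome definition but belongs to the null of the margin test. The 4.75% figure is a calculation against zero. Methods: Primary Aims puts the unmargined test first and adds the margin interval without ranking them.

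A reader might infer three stronger things that the documents do not support.
- **That the rules are incompatible.** They are nested. They agree below 5.0% and above the upper edge, and that edge is not fixed at 8.3%.
- **That the band holds the most likely results of a device that works as hoped.** The plan gives no expected TBWL difference for this device. Its 6.33% is a power scenario, and at a true 9.75% only about 20% of trials would fall in the band.
- **That the rule would be picked after unblinding.** The wording leaves that possible, but nothing describes it.

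**Conclusion.** The point holds as a gap in pre-specification: the three places do not give one decision rule for the TBWL primary. At the planning values the rules give opposite verdicts for observed differences from 5.0% to about 8.3%. At a true 6.33%, about two trials in three would meet the outcome definition and fail the margin test.

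This rests on reading the outcome definition as an estimate of at least 5% plus significance against zero, which is its natural sense but not its only possible one. The upper edge also rests on the planning SD and on 60/30 analysed, and in the trial it will follow the realised standard error.

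The power text does not show which rule was meant. The 4.75% belongs to a plain test against zero. At 6.33% the margin test has 12% power, not 80%, while the outcome definition has 78.6%. That is compatible with the two rules having been mixed, but the origin of 6.33% cannot be established from the documents.

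**What to change.** Before unblinding, state one deciding rule identically in Primary Outcome Measures, Methods: Primary Aims and Power Calculation. Label the other analysis supportive, and restate the power for the chosen rule.

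- **Default: keep the only written hypothesis.** Reword the outcome definition to require a lower one-sided 97.5% confidence limit above 5%. Say in Methods: Primary Aims that this test decides and that the unmargined t-test is supportive. State that, at the planning SD and 60/30, about 8.3% must be observed and 80% power needs a true difference of about 9.75%. Remove or correct the 4.75% and 6.33% statements.
- **Alternative: if the sponsor intends a test against zero plus an observed difference of at least 5%.** Rewrite H0 and H1 to say so, and report the confidence limit against 5% as supportive. State that 80% power needs about 6.4%, not 4.75%: a true 4.75% would meet this rule only 44% of the time. This is weaker than the hypothesis now written, so it should be made as an explicit, dated decision, given that 24 subjects had already been enrolled at the time of the Progress Report.

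The cost is protocol and SAP wording plus a restated power paragraph. The downside is that the stated detectable difference becomes less favourable under either rule, and any claim must then follow the one rule chosen.

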Based on the survey of adverse events devised by Utz et al. (2011) occurrence of the following adverse events will be specifically enquired about by the study coordinators during contact with the participants: headache; pain behind the ears; vertigo/ dizziness; blurred vision; nausea; fatigue/ tiredness; seizures; tinnitus; and other symptoms. The coordinators will ask and record whether these symptoms occur: never; almost never; sometimes; almost every time; or every time. And they will ascertain whether they occur while wearing the device, after wearing it, or both. Also, the coordinator will additionally ask whether the participants ever notice skin irritation after wearing the device.

We will monitor each instance of an adverse event causing a dropout from the study. The dropouts, together with causes, will be recorded and reviewed at the end of the study. This guidance from the FDA will be followed: <https://www.fda.gov/downloads/RegulatoryInformation/Guidances/UCM126572.pdf>. If it becomes evident that the proportion of subjects who drop out due to safety concerns/ adverse events convincingly exceeds 30%, the study will be halted.

Hearing Test and Ear Examination

The FDA provided feedback that some study participants should undergo a hearing test and otoscope examination of the ear canal. The FDA were aware that the study had started at this point and as discussed with the FDA there is no suggestion from any of the literature looking at the safety of GVS that hearing or the ear canal are adversely affected (Krystal et al., 2010; Marshall et al., 2010). And that a study specifically looking at the impact of GVS on cochlear function showed no effect (Cevette et al., 2012). Nonetheless, although there is no suggestion that hearing is adversely affected the FDA are requesting that such tests be carried out before agreeing to approve the device.

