More recently Paneri et al. (2015) reviewed the safety of repeated sessions of transcranial electrical stimulation (tES), a term that they use to encompass both the transdermal electrical modulation of cranial nerves (i.e. as in VeNS) and transcranial direct current stimulation (tDCS) of the cerebral cortex. Based on studies of tES on patient groups with depression (Brunoni et al., 2013) and migraine (Magis et al., 2013), and an array of studies of tES on normal volunteers (Brunoni et al., 2011; Kessler et al., 2012; McIntire et al., 2014; Morales-Quezada et al., 2015; Nitsche et al., 2003; Poreisz et al., 2007; Raimundo et al., 2012; Russo et al., 2013; Tadini et al., 2011), together with theoretical assessments of tES (Bikson et al., 2009; Brunoni et al., 2012), they commented that the “safety and tolerability profile previously accumulated regarding extended use of tES in clinical populations is compelling and supports a low-risk or non-significant risk designation” (Paneri et al., 2015).

Paneri et al. (2015) also assessed the safety and tolerability of repeated tES across time in a group of 100 volunteers who were split into three groups. The first group received sham stimulation, the second tES at 2mA, and the third pulses of tES at between 5 to 7 mA (this is notably higher than the 1mA maximum we are proposing to use). A total of 1905 treatment sessions were carried out in total across the three groups. The authors report no serious adverse events in any treatment condition, and that the common side effects were restricted to skin tingling, itching, and mild burning. Moreover, the incidence of these events were not statistically higher in the tES groups (Paneri et al., 2015). These mild skin sensations were not associated with withdrawal from the study and the authors report they became less salient after the first few sessions. Other adverse events, such as headache, were rare (<5%) and statistically indistinguishable across the three groups. Paneri et al. (2015) concluded that the “repeated use of limited output tES across extended periods, is well tolerated and poses no significant risks to healthy subjects, as previously observed in clinical studies”.

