This conclusion is in keeping with the findings of Wilkinson et al. (2009), who reported on a stroke patient who received repeated VeNS sessions as part of his rehabilitation therapy. The authors observed no adverse events during stimulation over 5 consecutive daily sessions of VeNS at 1mA for 30 minutes per day. Utz et al. (2011) studied the adverse effects of 255 VeNS sessions at 1.5mA (again higher than the 1mA we propose to use) in 55 stroke patients and 30 healthy controls. They found only a few mild adverse effects, with the most common being slight itching (mean 10.2%) and tingling (mean 10.7%) underneath the electrodes. They concluded that VeNS induces “very few and mild adverse effects in healthy and persons with stroke and [is] safe” (Utz et al., 2011). There is thus a body of literature supporting the safe usage of both tES and specifically VeNS devices delivering at least 1mA in stimulation.

Similarly, in February 2016, Halo Neuroscience, a company based in San Francisco, released additional data on the safety of tES; on this occasion for a 2mA tDCS device used on 1010 subjects.¹ They state that "there were zero reports of burn or seizure activity across all 1010 subjects, zero serious or unexpected adverse effects and zero withdrawals due to adverse events other than unpleasant sensation". They conclude that their tES study showed "a favorable safety profile and [was] associated with a very low incidence of adverse events, with no unexpected or serious adverse events".

Specific measures taken to reduce the incidence of skin irritation are the 32mm diameter of the electrodes, which are themselves hypo-allergenic, and the 50% duty cycle (i.e. half the time no current at all is being delivered), and the maximum current of 1.0mA. This means that the maximum phase current that can be delivered is only 500 μ C. In conclusion, there is not a significant risk of harm from using the device, and as such criteria d and g do not apply. Thus as the device does not meet the criteria of a SR device it is a NSR device.

References

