14. POTENTIAL RISKS

General Risks

1. Information of a personal nature will be collected in order to determine eligibility for the study, and therefore there is a risk of loss confidentiality.
2. Subjects may experience some degree of distress or anxiety due to confusion, the personal nature of

the questions, the VeNS, or their disqualification based on the exclusion criteria.

Risks relating to Screen Visit

There is a risk in the Screen Visit that a diagnosis of diabetes mellitus may be suggested.

Risks related to VeNS

A risk assessment for the device has been carried out (see Section 9 above) which indicates that it is a non-significant risk device. Due to the low current (1mA) and voltage (4.25 V), the VeNS stimulator being used in the study is safe. However, the following specific risks do exist:

1. Skin irritation at the electrode sites.
2. That the stimulation sites may be uncomfortable at the time of stimulation – an electrical tingling sensation may occur and also VeNS may induce the sensation of being pushed towards the side of the cathode.
3. A sensation of disequilibrium, analogous to being on a boat, may occur during the test that some subjects find uncomfortable.
4. VeNS may induce nausea.
5. VeNS may occasionally induce vomiting.
6. Headache has been reported to occur by Utz et al. 2011 as a side-effect from VeNS, but in all cases was mild and self-limiting.

Risks related to DXA Scanning

1. It has been calculated that subjects will be exposed to a combined total radiation dose of 0.18000mSv from the four whole body scans they will receive over the course of a year participating in the study. The scanner used at the ACTRI is a Hologic Discovery W DXA scanner, and the scans administered will be whole body scans in Array mode. Ionizing radiation is known to carry a dose related increased risk of cancer.
2. The scan sequences we are proposing to use were selected to provide the greatest possible information about body mass composition while exposing the subjects to the lowest possible dose of ionizing radiation. We note in this regard that the total dose we are proposing over the one year period of the study is less than the average background from living in San Diego for a year which is 1.6 mSv.
3. In order for the DXA scanner to function properly all metal must be removed from the subjects' bodies and they must change into a hospital gown. Some subjects may find doing so to be embarrassing or uncomfortable.

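### The solicited adverse-event list does not name itching, tingling or vomiting and leaves skin irritation off its graded scale, so effects the protocol itself expects may be under-recorded

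*Combined protocol and SAP*

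**What the plan says.** Section 9, Safety Endpoints and Adverse Event Monitoring, takes its list from a survey used in a cited vestibular-stimulation study. Coordinators ask about "headache; pain behind the ears; vertigo/ dizziness; blurred vision; nausea; fatigue/ tiredness; seizures; tinnitus; and other symptoms". Each is recorded on a five-level frequency scale ("never; almost never; sometimes; almost every time; or every time") and by timing: during wear, after it, or both. A separate sentence adds that "the coordinator will additionally ask whether the participants ever notice skin irritation after wearing the device". No frequency grade is given for that question, and it does not cover irritation during wear.

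Appendix 1, Risk Assessment, summarises the same vestibular-stimulation study as finding few and mild effects, "with the most common being slight itching (mean 10.2%) and tingling (mean 10.7%) underneath the electrodes". For a second study, of transcranial electrical stimulation, it says that "the common side effects were restricted to skin tingling, itching, and mild burning". Section 14, Risks related to VeNS, puts skin irritation first, mentions a tingling sensation during stimulation, and states that "VeNS may occasionally induce vomiting".

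Section 6 makes safety relative to control, including the occurrence of adverse events, the secondary objective, in a study meant to support regulatory submissions.

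**The concern.** A named item is put to every participant at every contact. An unnamed effect is recorded only if the participant thinks to mention it when asked about anything else. Here the named items include seizures and blurred vision, while the two effects that the survey's source study found most often are left to the open item. A safety table built this way could give well-ascertained rates for rare events and poorly ascertained rates for common ones.

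Skin irritation raises a narrower issue. It is asked about, but with less detail than any listed symptom, although Device Use Procedure makes it the one event with its own route to review and withdrawal. At stake is how accurately the submission describes tolerability.

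**Working it through.** **Step 1: set the lists side by side.**

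| Effect | Where the protocol names it | How Section 9 asks about it |
|---|---|---|
| Itching under electrodes | Appendix 1: 10.2% (vestibular study); also the transcranial study | Not named; open item only |
| Tingling under electrodes | Appendix 1: 10.7% (vestibular study); also the transcranial study; Section 14 | Not named; open item only |
| Mild burning | Appendix 1: transcranial study only (2 mA, and pulses of 5 to 7 mA) | Not named; open item, or perhaps the item on pain behind the ears |
| Vomiting | Section 14, as occasional | Not named; nausea is |
| Skin irritation | Section 14, first risk | Separate ever/never question, after wear only |
| Headache, nausea, disequilibrium | Section 14 | Named, graded and timed (disequilibrium as vertigo/dizziness) |

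The mismatch is plain from the text. Support is strongest for itching and tingling and weaker for burning and vomiting.

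**Step 2: other routes of capture.** Skin is inspected at every site visit, but inspection cannot show itching or tingling. Participants complete an adverse-event questionnaire at 3, 6 and 12 months; its items are not reproduced. Before month 3 the scheduled contacts are telephone calls at week 2 and month 1. Appendix 1 reports that skin sensations in the transcranial study became less noticeable after the first few sessions, so early contacts matter most.

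**Step 3: illustration of size.** The plan states no sample size or power for safety, so there is no figure to reproduce. Inputs: 60 active and 30 sham (Power Calculation); 10.2% and 10.7% (Appendix 1). Assumptions: the rates apply per participant, sham is 0%, and a fraction c of cases is recorded. Expected recorded active cases = 60 × rate × c. Power is for a two-sided Fisher's exact test at 0.05, by exact enumeration; Fisher's test is the plan's method for categorical secondary variables.

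| c (assumed) | Itching: cases | Power | Tingling: cases | Power |
|---|---|---|---|---|
| 100% | 60 × 0.102 = 6.1 | 27% | 60 × 0.107 = 6.4 | 31% |
| 75% | 4.6 | 9% | 4.8 | 11% |
| 50% | 3.1 | 1% | 3.2 | 1% |
| 25% | 1.5 | 0% | 1.6 | 0% |

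With a sham rate of 2%, power at full capture falls to 15% and 17%. With 0 of 30 in sham, at least 8 of 60 active cases are needed for p ≤ 0.05 (8 of 60 gives p = 0.048). Even perfect recording would thus not make this a useful significance test. The gain is in description and estimation.

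**Step 4: limits of the inputs.** The cited rates come from 255 sessions at 1.5 mA in 55 + 30 = 85 people, which is 255 / 85 = 3 sessions each on average. Appendix 1 does not say whether the percentages are per person or per session. Here the maximum is 1.0 mA, and a participant using the device five times a week for a year has about 5 × 52 = 260 sessions. The figures show scale only.

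**The case against.** The strongest reply is that nothing is shown to be lost. The open item is one of those specifically asked about and carries the same frequency and timing scale. Some burning may be reported as pain behind the ears. The questionnaire may already contain the missing terms. This stands: the documents support saying that the effects may be under-recorded, not that they will be.

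Second, a reader might infer that the loss falls mainly on the active arm, because the sham delivers no current. That is plausible for tingling, but the documents do not establish it. Appendix 1 says the skin effects were not statistically more frequent with active stimulation than with sham in the transcranial study. Both arms also use hydrogel electrodes and alcohol wipes, which could themselves cause itching, and both are asked the same questions.

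Third, skin irritation is well covered: its own question, inspection at each visit, a contact number and an arranged review. An ever/never question does count occurrence, which is what Section 6 asks for. What is missing is the frequency grade and any question about irritation confined to wear time.

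Fourth, a reader might infer that severity is never recorded. The symptom scale has no severity grade, but Appendix 6 places the good clinical practice processes in a separate appendix that is not available here, so that inference is not safe.

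What survives is the mismatch between the named list and the protocol's own account of expected effects.

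**Conclusion.** The point holds as a cheap improvement to a stated objective, not as a demonstrated bias. Itching and tingling should be named because the list's own source found them most often. Vomiting and burning have a lesser claim. Skin irritation should be recorded as fully as the listed symptoms.

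If the cited rates apply per participant, roughly 6 active cases of each sensation depend on the open item. It would be tempting to state how many of these will be missed, but every capture rate used above is an assumption. The size and direction of any between-arm bias cannot be derived from the documents.

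**What to change.** In both arms:

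- Add two named items: itching or tingling (or burning) under the electrodes, and vomiting.
- Put skin irritation on the existing frequency and timing scale (while wearing, after, both).
- Use the same items on the visit questionnaire and at the telephone contacts. If the questionnaire already has them, align Section 9 with it.
- Keep the answers from staff who weigh, counsel or assess outcomes. For telephone contacts, someone outside those roles has to take and hold the answers.

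The cost is a revised questionnaire page, an IRB amendment and some separation of staff duties, with no new visits. The main downside is that an answer about tingling could hint at allocation. Section 15 already has the discomforts of stimulation described to participants beforehand, so the question tells them little that is new, but staff still need shielding.

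Participants enrolled earlier will have the old items for past contacts, so record which form was used. Section 8 reports 24 enrolled against the 106 planned, and hearing tests were added mid-study in the same way, with earlier participants joining at later visits.
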